1.3 Preclinical Data

1.3.1 Pharmacology studies (non-GLP)

The following studies (performed with a non-GMP batch of ABY-029) confirm that fluorescently labeled anti-EGFR Affibody molecules delineate tumor margins better than a fluorescently labeled anti-EGFR antibody. [37,38]

- **Target binding assay (Biacore)**

Using 3 human tumor models with varying EGFR positive expression, and 1 EGFR negative tumor line for rats, Dartmouth determined the EGFR concentration in each tumor model using ABY-029, along with a simultaneously delivered reference agent (control affibody-IRDye680RD conjugate). We found that *in vivo* receptor concentration, calculated through receptor concentration imaging (RCI), was strongly correlated with *ex vivo* pathologist-scored immunohistochemistry and computer-quantified *ex vivo* immuno-fluorescence. Weak correlation was observed with *ex vivo* Western blot or *in vitro* flow cytometry assays.

- **Cell binding assays**

- **Isolated receptor binding assay**

The dissociation constant (KD) and receptor-ligand binding on and off rates (Kon and Koff) were determined using surface plasmon resonance (Biacore, GE Life Sciences). Sensograms were acquired and evaluated using the Biacore evaluation software to determine Kon and Koff using a 1:1 binding ratio kinetic fitting scheme. The KD value was subsequently calculated using the experimentally determined rate constants. We demonstrated that the binding affinity of anti-EGFR Affibody with IRDye 800 CW with human and rat EGFR was maintained as compared with anti-EGFR Affibody alone.

- **EGFR phosphorylation assay**

LI-COR Biosciences conducted a study in 2010 in which they labelled an EGFR-specific Affibody molecule (Eaff) with IRDye800CW maleimide and tested the molecular binding in cell culture and xenograft mouse tumor models. This study showed the dye labelled Affibody was bound and taken up specifically by EGFR-overexpressing tumor cells. When the fluorescent molecule was intravenously injected into nude mice with xenograft tumors, the tumor could be identified 1 hour after injection and was prominent after 1 day. Following dissection of tissue sections, they saw the labelled molecule accumulated highest in the liver, followed by the tumor and kidney. This study demonstrated that an Affibody labelled with a NIR fluorophore holds promise as a molecular imaging agent for EGFR-overexpressing tumors.

- **In vitro cytotoxicity study**

Phototoxic potential of the infrared light source when cells are exposed to ABY-029 was evaluated, compared to a known FDA approved phototoxic agent benzoporphyrin derivative monoacid A (BPD-MA) and found to be negligible.

- **Imaging study for localization in U251 orthotopic xenograft glioma in mice and rats**

Rats or mice were inoculated with orthotopic implantations of a human glioma cell line (U251, F98 or F98-EGFR) or with PBS (control) in the brain. Tumors were allowed to grow for 2 – 3 weeks before carrying out fluorescent tracer experiments.

We demonstrated that ABY-029 penetrated further into the margin of a U251 orthotopic xenograft mouse model than did a fluorescently labelled antibody (IRDye 680RD-Erbilux) (Sexton et al, PLoS One 2013). Longitudinal imaging of mice bearing U251 xenografts grown orthotopically in the brain was performed by tracking the uptake and retention over 0-3 hours in order to mimic *in vivo* imaging in humans. A reference tracer composed of a non-specific Affibody molecule bound to IRDye 680RD (LI-COR Biosciences, Inc) was used to quantify blood vessel leakage versus ABY-029 binding to the tumor. We also quantified the

tumor to normal brain uptake as a function of time, and compared these results to direct fiber optic probe measurements *in situ* and *ex vivo*. We validated the concept that sufficiently high signal to noise is achievable for ABY-029 uptake in the xenograft tumor model for microdose injection levels. This study suggests that microdoses of the compound will be detectable via imaging in human studies.

We used the U251 orthotopic xenograft rat model to demonstrate that distribution and uptake of microdose levels of ABY-029 is heterogeneous within a tumor, and that high fluorescing regions closely match with highly overexpressing regions of EGFR, as determined by immunohistochemistry (D'Souza et al, submitted 2016). We evaluated the uptake of the preGMP batch of ABY-029 in glioma after intravenous injection in normal rats. Fluorescent imaging of *ex vivo* brain slices from rats was conducted at different time points after ABY-029 administration (1 h – 48 h) to verify which time points provided maximal tumor to normal contrast. Although U251 tumor was most clearly visualized 1 hour after ABY-029 injection, tumors could be differentiated from the background after 48 hours. These results suggest that ABY-029 shows excellent potential to increase surgical visualization of confirmed EGFR positive tumors, with tumor to normal tissue contrast levels between 10 and 15.

We compared uptake of pre-GMP ABY-029 and in orthotopic rat model using both an EGFR negative tumor, F98, and EGFR positive tumor line, F98-EGFR, which was transfected with EGFR. In addition, we compare the uptake of ABY-029 with protoporphyrin IX (PpIX, administered as 5-aminolevulinic acid, ALA), a fluorophore currently under investigation for surgical guidance during glioma resection at Dartmouth College, and the standard of care for glioma patients in Germany. It was shown that in the EGFR positive tumor (F98-EGFR) ABY-029 outperforms PpIX in both the bulk and the margins of the tumors, while they performed the same in the bulk EGFR negative tumor (F98) and PpIX showed a slight advantage in the margin of the EGFR tumor (Elliott et al, 2016 submitted). These results show a clear indication that ABY-029 provides a surgical advantage in EGFR positive tumors.

1.3.2 Toxicology study (GLP)

The preclinical toxicology assessment is based on a single-dose toxicity study in one species conducted at Dartmouth.

• Extended single-dose Safety Study in rats

We conducted a definitive, extended single-dose toxicity study of ABY-029 in Sprague-Dawley rats, consistent with the principles outlined in "Guidance for Industry, Investigators, and Reviewers: Exploratory IND Studies" (2006). This study used the non-GMP-manufactured ABY-029 batch created at UAB, which was also used to develop the GMP process.

A maximum microdose is 30 nmol per 60 kg human subject (or ~237 µg for a protein drug, or 3.95 µg/kg in a human), and this study used the equivalent rat dose of 4.898 µg for a 0.20 kg rat (allowing for a 6.2X rat-to-human correction for skin surface area). Following review of FDA guidelines and pre-IND meetings with FDA, doses of 10X, 100X and 1000X were studied to evaluate whether pharmacologically relevant effects exist. The dose levels tested were 0.049 mg, 0.49 mg and 4.9 mg in the rat toxicity study, along with a control group.

Total Study Duration	1 day and 14 day post-injections
Recovery	Control and high dose group, sacrifice and analysis on day 15
Route	IV (bolus)
Frequency of dose	single
No of doses	1
Groups	Control and 3 dose groups
No of animals	6 male + 6 female per group
Dose levels (preliminary)	0 µg/kg 244.9 µg/kg 2449 µg/kg 24490 µg/kg

Main study	Day 0 - ABY-029 administration
Recovery period	1 or 14 days
Analysis	All standard parameters: Clinical signs, post-dosing observations, standard ophthalmology, body weight, haematology, bone marrow smears, clinical chemistry, macroscopic examination and organ weights, histopathology

A comprehensive set of protocol tissues was collected during necropsy and sent to a veterinary pathologist for microscopic examination. No histopathologic evidence of systemic toxicity was associated with the single-dose (10X, 100X, 1000X) intravenous administration of ABY-029 after 24 hours or 14 days in the study rats. Further, no toxic effects were observed among any of the animals during the routine daily checks.

- Biodistribution Study in normal rats**

Biodistribution of the 100X microdose of ABY-029 was assessed in normal rats and analysis was performed at 1 hour after injection. One hour post-intravenous administration of ABY-029 the rats were sacrificed by cervical dislocation, and the organs of interest were removed and then imaged on the Pearl Imaging System (LI-COR Biosciences). We found a high accumulation of ABY-029 in the liver, skin, lungs, and kidney, which are all organs with high endogenous EGFR expression and/or that are involved in the route of excretion. No significant difference occurred between ABY-029 accumulation in male and female non-sex organs, although males had slightly higher values, possibly due to size of organ versus body weight, as injected dose was normalized to body weight. Rats without brain tumors had comparably very low levels of ABY-029 accumulation in normal brain tissue, due to the blood brain barrier.

- Pharmacokinetic Study in normal rats**

Plasma pharmacokinetics of the dye was assessed as function of time by sampling blood from a jugular vein catheter at various time points after administration. Pharmacokinetic data was collected from normal Sprague Dawley rats at time points from 1 minute to 48 hour) after intravenous injection of 100X microdose ABY-029 (244.9 µg/kg). Blood plasma was read on a Fluoromax-3 fluorimeter (Horiba Jobin Yvon), a standard curve was created, and all fluorescent data was converted to concentration using the standard curve and the bi-exponential plasma curve. The plasma curve created in this study matched closely with the previously determined pre-clinical plasma curves, indicating that the physical and biological characteristics of ABY-029 were closely retained. The plasma half-life of ABY-029 in normal rats is approximately 15-20 minutes and less than 10% remains in the plasma at 24 hours and is undetectable at 48 hours. In pre-clinical rat and mouse studies, ABY-029 has been detectable in tissues (tumor, liver, kidney) for up to 72 hours.

1.4 Clinical Data to Date

While no clinical data is available to date on the experimental investigational product, the component molecules Z03115-Cys and IRDye800CW have been used in clinical trials, and products similar to ABY-029 have gone to clinical trial as well.

1.4.1 Related Affibody product ABY-025

ABY-025 (Z_{HER2:2891}-Cys-MMA-DOTA), is a HER2-specific Affibody® molecule that targets a radionuclide to HER2-receptor expressing tumors, for in vivo diagnosis of HER2-expressing cancer. ABY-025 is a 61 amino acid peptide that is modified site-specifically with one DOTA molecule at the side chain of the C-terminal cysteine. DOTA acts as chelator for the radionuclide Indium-111 (¹¹¹In) or Gallium-68 (⁶⁸Ga). An Investigational Medicinal Product Dossier (IMPD) for ABY-025 labeling with ⁶⁸Ga or ¹¹¹In has been filed for clinical studies in Sweden and Denmark, as outlined below.

- 1) ABY-025-MI103 (EudraCT 2010-021078-12, NCT01216033)

An exploratory study to evaluate the distribution of [¹¹¹In]ABY-025 uptake for SPECT imaging in subjects with metastatic breast cancer. This study included 7 patients and was completed in Sweden in 2011, with results published [39]

- 2) ABY-025-MI105 (EudraCT 2012-005228-14, NCT01858116).
An exploratory study to evaluate [⁶⁸Ga]ABY-025 for PET imaging of HER2 expression in subjects with metastatic breast cancer was due to have been completed in December 2014. This study was initiated 2013 in Swede68n and 16 patients were enrolled to receive at least 2 doses of ABY-025. No adverse events with possible or probable relationships to the study drug were reported, and seven non-serious adverse events with “unlikely” relationships to the study drug were noted [40].
- 3) MA 1021 (EudraCT 2010-024353-36, NCT02095210)
An exploratory study of HER2 PET imaging in breast cancer patients using [⁶⁸Ga]ABY-025 was completed. This study was conducted in Denmark from October 2010 to April 2013 with 8 patients enrolled. Results have been published [41]

1.4.2 IRDye 800CW in Clinical Trials

As of March 31, 2016, seven trials are listed on <http://clinicaltrials.gov/> involving the use of IRDye 800CW, two that were completed and five are ongoing with patients being recruited.

- 1) A Phase 1 study was completed (NCT01508572) ([VEGF-targeted Fluorescent Tracer Imaging in Breast Cancer](#)) (Oct 2011 – Sept 2012), using a VEGF targeted fluorescent tracer to breast cancer, imaging with diffuse tomography, opto-acoustic tomography and fluorescence reflectance imaging, with administration of 4.5 mg of bevacizumab-IRDye800 at 1-3 days prior to imaging. The trial enrolled 20 subjects total beginning in October 2011 and was completed in January 2015, but no results have been published.
- 2) A Phase 1 study was completed (NCT 02113202) ([Molecular Fluorescence Endoscopy in Patients with Familial Adenomatous Polyposis, Using Bevacizumab-IRDye800CW](#)) between March 2014 and January 2016. Seventeen patients with Familial Adenomatous Polyposis were administered Bevacizumab-IRDye800 at 4.5mg, 10mg or 25mg at 1-3 days prior to endoscopy. The study's primary objective was to determine the sensitivity of the fluorescent tracer bevacizumab-IRDye800CW, a NIR fluorescence endoscopy platform, in identifying adenomatous polyps. Results have not been published.
- 3) A Phase 1 study is recruiting patients (NCT 01972373) ([Visualization of Rectal Cancer During Endoscopy, Using a Fluorescent Tracer](#)), as of 2014, imaging rectal cancer with endoscopy and optical tomography methods, using two imaging sessions, each with a dose of 4.5mg of Bevacizumab-IRDye800, imaged before and then again 3 weeks after the initiation of chemotherapy. In these cases fluorescence imaging is performed 2 days after administration of the conjugate. 30 patients were estimated for enrolment.
- 4) Another Groningen study is a Phase 1 trial for esophageal imaging (NCT 02129933) ([VEGF-targeted Fluorescence Near-Infrared \(NIR\) Endoscopy in \(Pre\)Malignant Esophageal Lesions](#)), approved for April 2014 – June 2016. In this study, 4.5 mg of Bevacizumab-IRDye800 is given by IV at 2 days prior to fluorescence endoscopy imaging in 10 patients.
- 5) An ongoing Phase 1 trial in the United States with IRDye800CW targeted to the EGF receptor, (NCT 01987375) ([Cetuximab IRDye800 Study as an Optical Imaging Agent to Detect Cancer during Surgical Procedures](#)) is a dose escalation trial at the University of Alabama Birmingham. Head and Neck cancer is imaged during surgery, with Cetuximab-IRDye800CW conjugate as the administered agent. This study is directed by [name], planned for November 2015 – December 2016. Fifteen patients must be shown to tolerate a test dose of unlabelled Cetuximab of 100 mg, in the week prior to entering this study. The second phase of this study will reduce the test dose to 10 mg.

- 6) Radboud University in the Netherlands is conducting a Phase 1 trial (NCT 02497599) ([Intraoperative Dual-modality Imaging in Renal Cell Carcinoma](#)) with Indium-111-DOTA-girentuximab-IRDye800CW in renal cell carcinoma patients. The study will assess the feasibility and safety of intraoperative dual-modality imaging with Indium-111-DOTA-girentuximab-IRDye800CW in 22 patients between June 2015 and December 2016. Patients will receive a single IV dose of the drug, followed by a whole body planar scan and SPECT/CT scan and a partial nephrectomy. The study will be extended by use of dual-modality imaging.
- 7) A Phase 1 and 2 study at the University Medical Center Groningen (NCT 02583568) ([Fluorescence Guided Surgery in Breast Cancer](#)) is recruiting patients. This study will enrol 26 patients from October 2015 to December 2016 to define the optimal dose of the fluorescent tracer Bevacizumab-IRDye800CW for intraoperative delineation of breast cancer tissue using an improved and optimized fluorescent tracer and camera system.

1.5 Dose Rationale

We plan a sample size of 6-12 patients in this open label, single center, clinical trial of ABY-029. Administration will occur as a single intravenous injection to subjects with recurrent glioma, approximately 1-3 hours prior to surgery. The protocol is not a safety study since no physiological effects are expected at microdose levels of ABY-029. Rather, doses have been selected to determine if a fluorescence signal can be detected by wide-field imaging technology with a signal-to-noise ratio of 10, which is considered necessary for subsequent assessment of diagnostic performance of ABY-029 as a tumor biomarker sufficient to guide surgical resection in the future. No diagnostic or therapeutic intent is proposed, and administration of the study drug is not intended to alter the extent of planned brain tumor resection during the surgical procedure.

Dosing Scheme: A single microdose of ABY-029 at 30 nanomoles (237 μ g) will be injected into the first 3 patients. If samples from these subjects meet successful iFI criteria (defined as SNR \geq 10 at locations of samples with EGFR pathology score \geq 1 based on histological staining), 3 more patients will be enrolled at the same dose, concluding the study with a total of 6 subjects. Otherwise, the ABY-029 dose in the next 3 patients will be increased to 3X (90 nanomoles, 711 μ g). If samples from these subjects meet successful iFI criteria, 3 more patients will be enrolled at the 3X dose, concluding the study with a total of 9 subjects. If iFI criteria are not met, the next 3 patients will be enrolled at 6X dose (180 nanomoles, 1.42 mg). If iFI criteria are met, 3 more patients will be enrolled at the 6X dose, concluding the study with a total of 12 subjects. If iFI criteria are not met in the first 3 patients at the 6X dose, enrollment will be stopped with a total of 9 subjects.

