Study Product, Dose, Route, Regimen	
Criteria for successful iFI are locations of all EGFR positive samples (defined as having a pathology score ≥ 1 based on histological staining) having a measurable signal (defined as SNR ≥ 10). A single microdose of ABY-029 at 30 nanomoles (237μg) will be injected into the first 3 patients. If samples from these subjects meet successful iFI criteria, 3 more patients will be enrolled at the same dose, concluding the study with a total of 6 subjects. Otherwise, the ABY-029 dose in the next 3 patients will be increased to 3X (90 nanomoles, 711 μg). If samples from these subjects meet successful iFI criteria, 3 more patients will be enrolled at the 3X dose, concluding the study with a total of 9 subjects. If iFI criteria are not met, the next 3 patients will be enrolled at 6X dose (180 nanomoles, 1.42 mg). If iFI criteria are met, 3 more patients will be enrolled the 6X dose, concluding the study with a total of 12 subjects. If iFI criteria are not met in the first 3 patients at the 6X dose, enrollment will be stopped with a total of 9 subjects.
 
Because of the microdosing levels used, the results of the Dartmouth Toxicity Study (at 10X, 100X, 1000X doses), and the safety profile of similar compounds (e.g. ABY-025), we do not anticipate any serious adverse events (SAEs) related to ABY-029.

Duration of administration	ABY-029 will be administered by IV injection on day of surgery, approximately 1-3 hours prior to the procedure.
Reference methods	Post-operative histopathology will serve as the gold standard.
Statistical Considerations	Repeated measures analyses of variance will be performed to account for multiple samples from each patient. Student's t-test will be used to evaluate ABY-029 fluorescence signal detection in tumor relative to normal brain with iFI and intraoperative probe. Empirical ROC curves and logistic regression analysis for clustered binary data will be used to evaluate the accuracy of ABY-029-specific fluorescence in discriminating between EGFR+ glioma tumor, EGFR- glioma tissue, and normal tissue when detected by iFI and/or intraoperative probe.

1 Introduction

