7.1 Sample Size Determination

Sample size determination is based on the primary objective of the study as a pilot assessment of fluorescence detection of ABY-029 localization in EGFR+ tumors with iFI. We estimate a minimum of 6, and more typically 12-16 specimens per case will be collected, and assume an average of 10 is available consistent with numbers in similar studies of ALA-induced PpIX fluorescence that have enrolled over 100 subjects. To assess the adequacy of this sample size, if only 3 patients are enrolled at a specific dose, the study will have 80% power to detect a difference in fluorescence signal mean in samples relative to normal brain as small as 3.3 standard deviations with a two-sided significance level of 0.05, and a difference in fluorescence signal mean in samples between two EGFR pathology scoring levels of 2.7 standard deviation with the same power and significance level (assuming samples are equally distributed between EGFR pathology scoring levels). If 6 patients are enrolled a one dose, the detectable difference in fluorescence signal mean in samples relative to normal brain drops to 1.4 standard deviations (at the same power and significance level) and to 1.8 standard deviations for differences in signal mean between two EGFR pathology scoring levels.

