7.2 Data and Statistical Analysis

The primary study objective is to relate ABY-029 fluorescence (resulting from a specific pre-surgical dose) measured by wide-field iFI to EGFR pathology score (based on IHC staining) of coregistered tissue specimens sampled at the same time points during surgery. Similar but more sensitive fluorescence data will be available from the intraoperative optical probe. A minimum of 3 patients will be enrolled at a given dose, and up to 6 patients may be enrolled at one dose, if iFI SNR requirements are met. Assuming 10 specimens are available for analysis on average from the surgical cases at a given dose (this value is consistent with average specimen counts in related ALA-induced PpIX studies which have enrolled more than 100 subjects), 30 specimens with corresponding probe signals and IHC pathological scoring will be available for analysis, and as many as 60 specimens may exist, if iFI SNR goals are achieved. Clustered

data analyses of variance will be performed to account for multiple samples from each patient. Student's t-test evaluation will be used to determine signal detectability relative to measurements in normal brain, and relative to the noise floor of the iFI system determined from laboratory measurements in phantoms. ANOVA will also be used to assess differences in signal means when stratified by EGFR pathology score (0 = no expression, 1 = low expression, 2 = medium expression, 3 = high expression). Pearson's and Spearman's rank correlations between iFI signal strength and EGFR pathology score will be computed. These analyses will be repeated for the optical probe data as well.

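### At an expanded dose the first three patients are selected for complete detection, yet all six are analysed as one sample, with no separate result for the three unselected patients

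*Combined protocol and SAP*

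**What the plan says.** The rule for expanding a dose is in the Study Summary (Study Product, Dose, Route, Regimen): "Criteria for successful iFI are locations of all EGFR positive samples" reaching SNR of at least 10. Section 1.5 repeats the scheme without the word for all, so the 100% requirement rests on the Study Summary.

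If the first three patients at the starting dose meet it, "3 more patients will be enrolled at the same dose, concluding the study with a total of 6 subjects". The rule is the same at the higher doses; at the top step, "If iFI criteria are met, 3 more patients will be enrolled the 6X dose, concluding the study with a total of 12 subjects". The one branch without expansion is failure at the top step: "If iFI criteria are not met in the first 3 patients at the 6X dose, enrollment will be stopped with a total of 9 subjects".

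No section applies the criterion to the expansion patients or to all six, or says how a miss among them would be reported.

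The analysis sections treat the six as one data set. Section 7.1, in SD units: "If 6 patients are enrolled a one dose, the detectable difference in fluorescence signal mean in samples relative to normal brain drops to 1.4". Section 7.2: "Assuming 10 specimens are available for analysis on average" per case, "as many as 60 specimens may exist, if iFI SNR goals are achieved". The planned analyses are t-tests against normal brain and against the system noise floor, ANOVA by EGFR score, and correlations. Section 7.2 specifies no proportion with SNR of at least 10, although the primary objective in Section 2 is defined by that threshold.

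**The concern.** The expansion criterion selects on the quantity that the primary objective asks about. In a study that expands, the first three patients are there because none of their EGFR-positive specimens fell below the threshold. Their detection rate is 100% whatever the true rate, and the lower tail of their signal has been cut off. Only the next three patients test the dose without selection.

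Pooling the six mixes a selected half with an unselected half. At stake are how often EGFR-positive tissue is reported as detectable at the final dose, and how far its mean signal is reported to lie above normal brain. Someone judging whether the dose is good enough for a later diagnostic study will see the result of an expanded study, and so the conditional figure.

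**Working it through.** **1. Do the plan's own figures pool the six?** Inputs from Section 7.1: 80% power, two-sided 0.05. For a one-sample (paired) t-test with the patient as unit, the detectable difference d solves P(T > t(0.975, n−1)) = 0.80, where T is noncentral t with n−1 degrees of freedom and noncentrality d√n.
- n = 6: d = 1.43 SD (plan 1.4; power at 1.4 SD is 78.1%).
- n = 3: d = 3.26 SD (plan 3.3; power at 3.3 SD is 80.7%).

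The six-patient figure is reproduced with all six as a single sample. The 60 specimens in Section 7.2 are likewise 6 × 10.

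**2. Bias in pooled detection, given expansion.** Let p be the true probability that an EGFR-positive specimen has SNR of at least 10 (assumed; not in the documents). Given expansion, the first three patients contribute exactly 1 and the next three contribute p on average. With equal numbers of EGFR-positive specimens in the two halves:

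E[pooled] = (1 + p)/2, and bias = (1 + p)/2 − p = (1 − p)/2.

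This holds whatever the within-patient correlation, because the later patients are independent of the first three.

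**3. How often would such a dose be expanded?** The number of EGFR-positive specimens is not given, so two values are shown. With independent specimens the chance per dose is p^30 (all 10 per patient positive) or p^15 (5 per patient).

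| p | Pooled mean | Expansion three | Bias (points) | p^30 | p^15 |
|---|---|---|---|---|---|
| 0.80 | 0.90 | 0.80 | 10 | 0.1% | 3.5% |
| 0.90 | 0.95 | 0.90 | 5 | 4.2% | 20.6% |
| 0.95 | 0.975 | 0.95 | 2.5 | 21.5% | 46.3% |
| 0.98 | 0.99 | 0.98 | 1 | 54.5% | 73.9% |

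Clustering makes expansion of a weaker dose more likely. In a beta-binomial model with 10 positive specimens per patient and intraclass correlation 0.5, p = 0.80 passes 15.5% of the time and p = 0.90 passes 40.5%. The pooled means stay at 0.90 and 0.95.

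**4. Averaged over the whole three-dose rule.** Take the same p at each dose and include studies that stop at the top step with three patients there. The final-dose estimate is then biased by +0.6 point at p = 0.95 with 30 independent specimens, and by +6.3 points at p = 0.70 with one specimen per patient.

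**5. Mean signal.** Illustration only: normal SNR with mean 15, SD 5, intraclass correlation 0.5 and 10 positive specimens per patient. Given expansion, the pooled mean is 16.5 and the expansion-only mean is 15.0.

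**6. Contrasts between EGFR scores.** Illustration only: mean SNR 8, 14, 17 and 20 for scores 0 to 3, SD 4, two specimens per score per patient. The true difference between scores 3 and 1 is 6.0. Pooled given expansion it is about 5.5 (correlation 0) or 5.8 (correlation 0.5), because the criterion trims score 1 most. The difference between scores 1 and 0, also truly 6.0, rises to about 6.6 or 6.2.

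**7. Precision of the unselected estimate.** If every patient is fully detected, the exact two-sided 95% lower bound is 0.025^(1/3) = 29% for 3 of 3, against a naive 0.025^(1/6) = 54% for 6 of 6.

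**The case against.** The strongest reply has four parts.

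- **The criterion governs enrolment only.** A reader might infer that the first three patients settle the primary conclusion and that later misses cannot alter it. The documents do not say so. No section declares a dose successful once the criterion is met, the objective and endpoint cover sampled tissue in general, and misses among the last three do enter the pooled analysis. This part stands.
- **No detection proportion is planned.** Correct: the detection figures apply to any pooled rate that is reported against the primary objective, not to a named estimate. The selection still raises mean signal in EGFR-positive tissue, and that does enter a planned t-test.
- **The large biases belong to doses that rarely expand.** With 18 independent EGFR-positive specimens, a dose with p = 0.70 passes with probability 0.7^18 = 0.16%, and one with p = 0.90 with 0.9^18 = 15%. This is right under independence. It weakens under clustering, which Section 7.2 itself anticipates by planning clustered analyses.
- **Resting the conclusion on three patients wastes data in a pilot.** This stands as an argument against an expansion-only primary result or a second all-or-nothing test: at p = 0.90 and six independent positive specimens per patient, at least one of the 18 expansion specimens would miss in 1 − 0.15 = 85% of expanded studies. It is no argument against showing the two sets of patients side by side.

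**Conclusion.** The point holds as a reporting weakness in the expansion branch. Given expansion, a pooled detection rate overstates the true rate by (1 − p)/2 on average: 10 points at p = 0.80, falling to 1 point at p = 0.98. This assumes equal numbers of EGFR-positive specimens in the two halves and stable conditions between them; p itself is assumed. Pooled mean signal in EGFR-positive tissue against normal brain is also raised, by an amount that the documents do not allow to be fixed.

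The practical effect is small when EGFR-positive specimens are many and independent, because a poor dose then seldom expands. It is larger when results cluster by patient or few specimens are EGFR positive.

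A reader might go further and infer that every analysis at the final dose is tilted upward. That is not supported: contrasts among scores 1 to 3 can shrink. The bias given expansion also does not describe a study that stops at the top step without expansion.

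**What to change.** In Section 7.2 and the Study Summary:

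1. Tabulate the SNR ≥ 10 result and the mean signal in EGFR-positive tissue separately for the three patients who triggered expansion and the three enrolled afterwards.
2. Name the later three as the unselected estimate for the dose.
3. Show the pooled six-patient results alongside, labelled as conditional on the first three having met the criterion.

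No new pass/fail rule is needed, and the expansion patients should not become the sole primary result. Dose steps and patient numbers stay as they are.

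The cost is some wording and one extra tabulation. The unselected estimate will be imprecise (lower bound 29% even if all three patients are fully detected) and may look less favourable than the pooled figure.
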